Safety monitoring will be conducted by an independent data monitoring committee (IDMC). The frequency of safety reviews will be defined in the IDMC charter. Minutes from the open meetings of the IDMC will be provided if requested by regulatory agencies. The function and membership of the IDMC will be described in the IDMC charter.

Sample Size Rationale

Phase 1 – Determination of the Maximum Tolerated Dose: The total number of subjects required for the Phase 1 portion of this study will depend upon the toxicities observed as the study progresses. The minimum number of evaluable subjects required is 4. The projected maximum number of evaluable subjects required is 48. Once the MTD or RP2D has been defined, up to 6 additional subjects with recurrent or refractory solid tumors may be enrolled to acquire PK data in a representative number of young subjects. Therefore, a maximum of 54 subjects are expected to be enrolled in the 4 dose escalation levels, and PK expansion. The Phase 1 part of the study is expected to be completed within 18 months. In the event that each of Dose Levels -1, 1, 2, and 3 are expanded to 12 subjects, an absolute maximum of 54 subjects would be required allowing for 20% to be non-evaluable and including up to 6 additional subjects for PK analysis.

Phase 2: Phase 2 will require a minimum of 10 evaluable subjects per disease cohort and a maximum of 20 (10 evaluable subjects in each stage of Simon's optimal 2-stage design). Therefore, a maximum of 22 subjects per cohort will be enrolled to allow for a 10% non-evaluable rate. This design has 88% power to detect a 20% increase in the response rate at the significance level of one-sided $\alpha = 0.07$ assuming a null response rate of 5% and alternative response rate $\geq 25\%$.

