Doses in the Dose Adjustment column are based on a presumed starting dose of 11 mg/m² lenvatinib and 3 mg/m² everolimus. Dose reductions will occur in succession based on the previous dose level. Each dose level reduction due to toxicity at a given BSA is approximately 25% reduction from the previous dose. Once the study drug dose has been reduced, it may not be increased at a later date, unless the dose was mistakenly decreased; in this situation, the sponsor’s approval is required to increase the dose.

Table 5 Dose Modification Guidelines for Lenvatinib-Everolimus Combination Treatment-Related Toxicity

Treatment-Related Toxicity ^{a,b}	Management	Dose Adjustment
Grade 1 or Tolerable Grade 2		
	Continue treatment	No change
Intolerable Grade 2^{c, d, e} or Grade 3^f		
First occurrence	Interrupt lenvatinib and everolimus until resolved to Grade 0-1 or tolerable Grade 2	Reduce lenvatinib dose to 8 mg/m ² (or approximately 25% reduction of the starting dose) orally once a day (one-level reduction) and resume everolimus at the same dose as prior to dose interruption
Second occurrence (same toxicity or new toxicity)	Interrupt lenvatinib and everolimus until resolved to Grade 0-1 or tolerable Grade 2	Reduce lenvatinib dose to 6 mg/m ² (or approximately 25% reduction from the previous dose level) once a day (one-level reduction). Dose reduction of everolimus to 3 mg/m ² every other day may be considered for Grade 3 toxicity ^c

Third occurrence (same toxicity or new toxicity)	Interrupt lenvatinib and everolimus until resolved to Grade 0-1 or tolerable Grade 2	Reduce lenvatinib dose to 4.5 mg/m ² (or approximately 25% reduction from the previous dose level) orally once a day (1-level reduction). Dose reduction of everolimus for Grade 3 toxicity: i) if 3 mg/m ² daily everolimus at event onset, reduce to 3 mg/m ² every other day or ii) if 3 mg/m ² every other day everolimus at event onset, discontinue
Fourth occurrence (same toxicity or new toxicity)	Interrupt lenvatinib and everolimus	Discuss with sponsor
Grade 4^g: Discontinue Study Treatment		

Note: For grading see [Common Terminology Criteria for Adverse Events \(CTCAE\) v4.03](#). Collect all CTC grades of adverse events, decreasing and increasing grade.

- a: An interruption of study treatment for more than 28 days will require sponsor's approval before treatment can be resumed.

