Phase 2 Cohorts 1 to 3 will use a 10+10 Simon's optimal 2-stage design for each cohort; 10 evaluable subjects will be enrolled to each stage. The Sponsor will closely monitor enrollment to ensure that at least 50% of subjects enrolled in each cohort are <18 years of age at the time of informed consent. The primary outcome measure for Ewing sarcoma/pPNET, rhabdomyosarcoma, and HGG will be ORR (complete or partial response) at 16 weeks. If there are no responses among the 10 subjects in Stage 1, then the enrollment to that disease cohort will stop and conclude that the lenvatinib/everolimus combination therapy does not elicit a response in that disease cohort. If there is at least 1 response in the first stage, then the second stage will enroll 10 additional evaluable subjects. If there are 2 or fewer responses among the 20 evaluable subjects, then lenvatinib/everolimus combination therapy will be declared a failure for that disease cohort. Subjects will meet the criteria for being evaluable for an objective response if they have measurable disease present at baseline and at least 1 post-baseline efficacy assessment, unless they have discontinued prior to the first efficacy assessment due to progressive disease. Subjects who are not evaluable for objective response will be replaced.

The Treatment Phase for each subject in Phase 2 ends after completing 4 cycles of treatment unless subject discontinues early. Those subjects who discontinue study treatment before completing 4 cycles transition to the Off-treatment Visit. Those who complete 4 cycles will transition to the Extension Phase. Study treatment and tumor assessments will continue during the Extension Phase.

Dosing Nomogram

The dose nomogram in [Table 3](#) provides the dose of lenvatinib to be administered for BSA increments starting from 0.6 m². BSA must be calculated on Day 1 of each cycle based on the subject's current height and body weight. The actual dose to be administered is rounded to the nearest whole number. The total lenvatinib dose is capped at 18 mg daily (Dose Levels -1 and 1), and at 24 mg (Dose Levels 2 and 3).

Table 3 Total Lenvatinib Dose (mg): Body Surface Area (m²) * Dose Level (mg/m²)

Lenvatinib Dose Levels							
8 mg/m ² Everolimus 3.0 mg/m ² Dose Level -1		11 mg/m ² Everolimus 3.0 mg/m ² Dose Level 1		14 mg/m ² (Everolimus 3.0 mg/m ²) Dose Level 2		14 mg/m ² (Everolimus 4.5 mg/m ²) Dose Level 3	

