9.4 Treatment

9.4.1 Treatment Administered

Lenvatinib will be provided as hard capsules containing 1 mg, 4 mg, or 10 mg lenvatinib. An extemporaneous suspension of lenvatinib capsules should be used for children unable to swallow capsules ([Appendix 12](#)).

Everolimus will be provided as 2 mg, 3 mg, and 5 mg dispersible tablet formulations (everolimus tablets for oral suspension).

Lenvatinib and everolimus will be administered orally on a once daily schedule in continuous 28-day cycles. The sequence of administration is not important. Dosing nomograms based on BSA and dose level will be used to prescribe lenvatinib and everolimus for subjects to minimize inter-subject dosing variability. The maximum daily dose of lenvatinib administered during the study should not exceed 18 mg in Dose Levels -1, and 1, and 24 mg in Dose Levels 2 and 3. The maximum daily dose of everolimus should not exceed 5 mg in Dose Levels -1, 1, and 2, and 7 mg in Dose Level 3. Intra-subject titration of everolimus will not be allowed on this study. Intra-subject dose escalation of both lenvatinib and everolimus will not be allowed.

Subjects benefiting from study treatment in the opinion of the investigator will continue treatment until disease progression, development of unacceptable toxicity, withdrawal of consent or are withdrawn from the study for any reason, or termination of the study by the sponsor.

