9.4.1.1 Study Treatment Dose Reduction and Interruption Instructions

Dose reduction and interruptions for subjects who experience lenvatinib-everolimus combination therapy-related toxicity will be managed as described in [Table 5](#). Investigators will decide the probability of the event being related to protocol therapy as to whether dose modification of drug therapy is required.

Doses in the Dose Adjustment column are based on a presumed starting dose of 11 mg/m² lenvatinib and 3 mg/m² everolimus. Dose reductions will occur in succession based on the previous dose level. Each dose level reduction due to toxicity at a given BSA is

approximately 25% reduction from the previous dose. Once the study drug dose has been reduced, it may not be increased at a later date, unless the dose was mistakenly decreased; in this situation, the sponsor's approval is required to increase the dose.

Asymptomatic laboratory abnormalities, including Grade ≥ 3 abnormalities (eg, elevations of amylase and lipase) that are not considered clinically relevant by the investigator, should be managed per institutional guidelines; continuation of treatment should be discussed with the sponsor.

Table 5 Dose Modification Guidelines for Lenvatinib-Everolimus Combination Treatment-Related Toxicity

Treatment-Related Toxicity ^{a,b}	Management	Dose Adjustment
Grade 1 or Tolerable Grade 2		
	Continue treatment	No change
Intolerable Grade 2^{c, d, e} or Grade 3^f		
First occurrence	Interrupt lenvatinib and everolimus until resolved to Grade 0-1 or tolerable Grade 2	Reduce lenvatinib dose to 8 mg/m ² (or approximately 25% reduction of the starting dose) orally once a day (one-level reduction) and resume everolimus at the same dose as prior to dose interruption
Second occurrence (same toxicity or new toxicity)	Interrupt lenvatinib and everolimus until resolved to Grade 0-1 or tolerable Grade 2	Reduce lenvatinib dose to 6 mg/m ² (or approximately 25% reduction from the previous dose level) once a day (one-level reduction). Dose reduction of everolimus to 3 mg/m ² every other day may be considered for Grade 3 toxicity ^e

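### For an 11 mg/m² start, Table 5's two wordings of the first lenvatinib reduction disagree in subjects at the Table 3 cap: read through Table 3, the step shrinks above BSA 1.8 m² and is nil from 2.19 m²

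*Protocol*

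**What the plan says.** The Synopsis and Protocol 9.4.1.1 introduce Table 5 with a general rule: "Each dose level reduction due to toxicity at a given BSA is approximately 25% reduction from the previous dose". They add the base from which the table is written: "Doses in the Dose Adjustment column are based on a presumed starting dose of 11 mg/m" (per square metre; the everolimus base is 3 mg/m²).

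For a first intolerable Grade 2 or Grade 3 toxicity, the Table 5 cell gives a level, "Reduce lenvatinib dose to 8 mg/m" (squared), and then an alternative in brackets, "or approximately 25% reduction of the starting dose". The second and third occurrences go to 6 and 4.5 mg/m², each with a similar bracketed percentage.

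Protocol 9.4.1 names the prescribing tool: "Dosing nomograms based on BSA and dose level will be used to prescribe lenvatinib and everolimus for subjects". Section 9.1 sets the limit in that tool: "The total lenvatinib dose is capped at 18 mg daily (Dose Levels -1 and 1"). In Table 3 the 11 mg/m² column reaches 18 mg at BSA 1.60 m² and the 8 mg/m² column reaches it at 2.19 m².

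Protocol 9.4.1.3 requires treatment interrupted for persistent severe hypertension to restart at a lower dose, defined as one Table 5 level.

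**The concern.** The two halves of the Table 5 cell are offered as equivalents. They are equivalent only while the administered dose is proportional to BSA. Once the starting dose is fixed at 18 mg by the cap, the 8 mg/m² dose goes on rising with BSA and catches up with it. The mg/m² instruction then delivers less and less of the stated cut, while the percentage instruction still delivers all of it.

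Two sites following the protocol could therefore restart the same large subject, after the same event, on clearly different lenvatinib doses. From BSA 2.19 m², the mg/m² route through Table 3 gives no reduction after Grade 3 toxicity. That contradicts the general rule and the lower dose that 9.4.1.3 requires on restart.

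The SAP inherits the ambiguity. Section 5.6.1.3 separates a reduction from an interruption by comparing dose levels before and after the break, with 11, 0, 8 mg/m² as its example of a reduction. An 18, 0, 18 mg sequence in a subject relabelled from 11 to 8 mg/m² is a reduction by nominal level and an interruption by milligrams.

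**Working it through.** **Inputs.** Levels 11, 8, 6 and 4.5 mg/m² and the percentage wording: Table 5. Milligram doses by BSA, rounding to whole milligrams, and the caps (18 mg for the 8 and 11 mg/m² levels, 24 mg for 14 mg/m²): Table 3 and 9.1. Everolimus doses: Table 4.

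**Formula.** Percentage reduction = 1 − new dose / old dose.

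**The plan's own figure.** On the mg/m² labels:
- 11 to 8: 1 − 8/11 = 27.3%
- 8 to 6: 1 − 6/8 = 25.0%
- 6 to 4.5: 1 − 4.5/6 = 25.0%

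So about 25% reproduces on that scale.

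**Table 3.** Rebuilding it as the smaller of the cap and BSA × level rounded to a whole milligram, in steps of 0.01 m² from 0.60 to 2.60 m², reproduces the 8, 11 and 14 mg/m² columns with no mismatch. The table itself is correct.

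**First reduction, both doses read from Table 3 (11 and 8 mg/m² columns).**

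| BSA (m²) | Start (mg) | Reduced (mg) | Reduction |
|---|---|---|---|
| 0.60–1.59 (uncapped) | 7–17 | 5–13 | 20.0% to 33.3% (rounding) |
| 1.60–1.68 | 18 | 13 | 27.8% |
| 1.69–1.81 | 18 | 14 | 22.2% |
| 1.82–1.93 | 18 | 15 | 16.7% |
| 1.94–2.06 | 18 | 16 | 11.1% |
| 2.07–2.18 | 18 | 17 | 5.6% |
| 2.19 or more | 18 | 18 | 0% |

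**Percentage wording at the cap.** 18 × 0.75 = 13.5 mg in every capped row. In whole milligrams this is 13 or 14 mg, a cut of 27.8% or 22.2%. The two wordings agree to within rounding up to 1.81 m² and part from 1.82 m². The uncapped rows never fall below 20%, so rounding does not explain the rows below 17%.

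**Later step.** Table 3 has no 6 mg/m² column. Taking BSA × 6, rounded: at 2.19 m², 13.14 becomes 13, so 18 to 13 mg (27.8%); at 2.31 m², 13.86 becomes 14, so 18 to 14 mg (22.2%); at 2.50 m², 18 to 15 mg (16.7%).

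**14 mg/m² start.** Reading Table 3's 14 and 11 mg/m² columns from BSA 1.68 m²: 24 to 18 mg, 1 − 18/24 = 25.0%.

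**Dose Levels 1 and -1.** From 2.19 m² both give 18 mg lenvatinib. Table 4 gives 5 mg everolimus from 1.50 m² at both levels. The two prescriptions are identical.

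**The case against.** The strongest reply is that a zero reduction is not what the protocol prescribes. The general rule is stated on the administered dose at a given BSA, the Table 5 cell carries a percentage alternative, and both lead to 13.5 mg. The 8 mg/m² column of Table 3 is headed as a Phase 1 cohort level, no sentence says that reduced doses are read from it, and the table has no columns for 6 or 4.5 mg/m². This stands to the extent that zero is one of two readings. It does not remove the conflict: the cell names 8 mg/m² first, the nomograms are named as the prescribing tool, and Table 3 prints a milligram answer for that level.

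Three stronger readings are tempting, and the documents do not support them.

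- A reader might infer that dose-reduction data in capped subjects cannot be interpreted. SAP 5.3.6.1 derives the actual dose level from daily dose and BSA and lists capped subjects, 5.6.1.2 summarises dose intensity from milligrams taken, and 5.6.1.3 lists all administration records. Only the counting rule is unclear.
- A reader might infer that Phase 1 de-escalation would re-treat a large subject at a dose already found too toxic. Under the rolling 6 design, Level -1 is given to a subsequent cohort, and tolerability is judged on the cohort. The narrower fact is that a newly enrolled subject of BSA 2.19 m² or more would receive the same doses at either level.
- A reader might infer that a 14 mg/m² start has the same defect. Table 3's own columns give exactly 25% there. A shrinking step needs an assumed 10.5 mg/m² level that keeps the 24 mg cap, and the documents state neither.

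Scope is also a fair objection. The shortfall begins at 1.82 m², and the second step is again about 22% to 28% between 2.19 and 2.31 m². No effect on the primary endpoint is shown.

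**Conclusion.** The inconsistency is real and conditional. For an 11 mg/m² start, if the reduced dose is read from Table 3, the first lenvatinib reduction is 16.7% at BSA 1.82–1.93 m², 11.1% at 1.94–2.06, 5.6% at 2.07–2.18 and nil from 2.19 m². The percentage wording in the same cell gives 13.5 mg. Neither document says which applies to a capped subject. No printed figure is miscalculated; the fault is that two instructions offered as equivalent are not equivalent at the cap.

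The number of subjects affected cannot be stated and may be small, since no BSA distribution is given. Such subjects are within scope: Table 3 prints rows up to 2.19 m² and above, eligibility sets a minimum BSA of 0.6 m² and no maximum, and Phase 2 admits subjects up to age 21. Because the rule acts after Grade 3 or intolerable Grade 2 toxicity, the passages must be reconciled. No view is taken on which dose is right.

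**What to change.** Reconcile Table 5 (Synopsis and 9.4.1.1) with the Table 3 caps so that the mg/m² level and the stated percentage lead to the same capsule dose in capped subjects. One way is a reduced-dose nomogram giving milligrams by BSA for each reduction step from each starting level, with the capped rows shown and the doses chosen by the sponsor and the Protocol Steering Committee. Make the restart text in 9.4.1.3 point to the reconciled table. Add a sentence in 9.1 on how Dose Level -1 applies to a new subject whose doses at Levels 1 and -1 are identical.

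In SAP 5.6.1.3, state whether a reduction in a capped subject is counted on actual milligrams or on nominal level, and align this with the actual dose level in 5.3.6.1.

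The cost is one table and a few sentences in an amendment and a SAP revision. No subjects, visits or procedures are added.

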17. Males who have not had a successful vasectomy (confirmed azoospermia) or if they and their female partners do not meet the criteria above (ie, not of childbearing potential or practicing highly effective contraception throughout the study period and for 7 days after lenvatinib discontinuation or 4 weeks after discontinuation of everolimus). No sperm donation is allowed during the study period and for 7 days after lenvatinib discontinuation or 4 weeks after discontinuation of everolimus.

Study Treatment

Study drugs: Lenvatinib will be provided as hard capsules containing 1 mg, 4 mg, or 10 mg lenvatinib. An extemporaneous suspension of lenvatinib capsules should be used for children unable to swallow capsules.

Everolimus will be provided as 2 mg, 3 mg, and 5 mg dispersible tablet formulations (everolimus tablets for oral suspension).

Lenvatinib and everolimus will be administered orally on a once daily schedule in continuous 28-day cycles. The sequence of administration is not important. Dosing nomograms based on BSA and dose level will be used to prescribe lenvatinib and everolimus for subjects to minimize inter-subject dosing variability. The maximum daily dose of lenvatinib administered during the study should not exceed 18 mg in Dose Levels -1, and 1, and 24 mg in Dose Levels 2 and 3. The maximum daily dose of everolimus should not exceed 5 mg in Dose Levels -1, 1, and 2, and 7 mg in Dose Level 3. Intra-subject titration of everolimus will not be allowed on this study. Intra-subject dose escalation will not be allowed.

Comparator Drug (if applicable): Not Applicable

Study Drug Dose Interruption and Reduction Instructions:

Dose reductions and interruptions for subjects who experience lenvatinib-everolimus combination therapy-related toxicity will be managed as described in Table 5. Investigators will decide the probability of the event being related to protocol therapy as to whether dose modification of drug therapy is required.

Asymptomatic laboratory abnormalities, including Grade ≥ 3 abnormalities (eg, elevations of amylase and lipase) that are not considered clinically relevant by the investigator, should be managed per institutional guidelines; continuation of treatment should be discussed with the sponsor.

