- b: Initiate optimal medical management for nausea, vomiting, hypothyroidism and/or diarrhea prior to any study treatment interruption or dose reduction.
- c: Applicable only to Grade 2 toxicities judged by the subject and/or physician to be intolerable.
- d: Obese subjects with weight loss do not need to return to the baseline weight or within 10% of baseline weight (ie, Grade 1 weight loss). These subjects will restart the study drug(s) at a lower dose once their weight remains stable for at least 1 week and they reached the normal body mass index (BMI; if the weight loss occurred, but it is still above normal BMI, they can restart the study treatment at a lower dose once the weight has been stable for at least 1 week). Normal BMI should be used as the new baseline for further dose reductions.
- e: For Grade 2 toxicity, resume everolimus at the same dose as prior to dose interruption. For Grade 3 toxicity, investigator will decide the probability of the event being related to one or both drugs as to whether dose modification of one or both drugs is required.
- f: For asymptomatic laboratory abnormalities, such as Grade ≥ 3 elevations of amylase and lipase that are not considered clinically relevant by the investigator, continuation of treatment should be discussed with the sponsor.
- g: Excluding laboratory abnormalities judged to be non-life-threatening, in which case manage as Grade 3.

Duration of Treatment

Study duration for each subject is estimated to be:

- **Pretreatment Phase:** 4 weeks
- **Treatment Phase:** 1 cycle (4 weeks) in Phase 1, 4 cycles (16 weeks) in Phase 2.
- **Extension Phase:** Estimated maximum time of treatment is 2 years (24 cycles)

Subjects may remain on study treatment as long as they do not meet any of the following criteria: 1) experience objective progression of disease (according to RECIST 1.1 or RANO criteria, as appropriate); 2) exhibit no clinical benefit (in the opinion of the investigator); 3) experience unacceptable toxicity leading to withdrawal from the study; 4) withdraw or are withdrawn from the study for any reason, or; 5) termination of the study program.

As long as the subject has not experienced intolerable toxicity, he or she can continue to receive study treatment. A 28-day follow-up visit from last date of receiving investigational drug will be performed for subjects who discontinue study treatment.

Concomitant Drug/Therapy

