9.4.1.7 Management of Non-Infectious Pneumonitis

Non-infectious pneumonitis is a recognized class effect of rapamycin derivatives, including everolimus. Non-infectious pneumonitis was described in 19% of subjects taking everolimus ([Afinitor package insert](#)). Some cases were severe and on rare occasions, a fatal outcome was observed. Investigators should therefore consider a diagnosis of non-infectious pneumonitis in subjects presenting with non-specific respiratory signs and symptoms and in whom infectious, neoplastic and other non-medicinal causes have been excluded by means of appropriate investigations.

Subjects who develop radiological changes suggestive of non-infectious pneumonitis and have few or no symptoms (Common Terminology Criteria for Adverse Events [CTCAE] Grade 1) may continue study dosing without dose adjustments.

1. If symptoms are moderate (CTCAE Grade 2):
 - Study treatment (lenvatinib-everolimus combination) should be interrupted and the use of corticosteroids may be indicated until symptoms abate (resolved to CTCAE Grade 0-1) and may then be restarted at the same doses prior to study treatment interruption.

- If Grade 2 non-infectious pneumonitis recurs despite optimal management, then study treatment administration should be interrupted and the use of corticosteroids may be indicated until symptoms abate (resolved to CTCAE Grade 0-1).
2. If symptoms are severe (CTCAE Grade 3):
 - Study treatment should be interrupted and the use of corticosteroids may be indicated until clinical symptoms resolve (to CTCAE Grade 0-1).
 3. If symptoms are life-threatening (CTCAE Grade 4):
 - Study medications should be discontinued.

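### For Grade 2 non-infectious pneumonitis judged tolerable, Table 5 says keep dosing and Section 9.4.1.7 says hold both drugs, and nothing states which rule governs

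*Protocol*

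**What the plan says.** The protocol synopsis, under the dose interruption and reduction instructions, states that "combination therapy-related toxicity will be managed as described in Table 5". Section 9.4.1.1 repeats the instruction. Neither place excepts any event.

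Table 5 has a row headed "Grade 1 or Tolerable Grade 2", with the action to continue and no dose change. The next row, for intolerable Grade 2 or Grade 3, reads "Interrupt lenvatinib and everolimus until resolved to Grade 0-1 or tolerable Grade 2" and at first occurrence takes lenvatinib down one level. Footnote c confines the Grade 2 part of that row: "Applicable only to Grade 2 toxicities judged by the subject and/or physician to be intolerable". The text introducing the table says of a reduced dose that "it may not be increased at a later date, unless the dose was mistakenly decreased", and then only with the sponsor's approval.

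Section 9.4.1.7 sets its own rules by grade. For Grade 2 its trigger is "If symptoms are moderate (CTCAE Grade 2" and its action is "Study treatment (lenvatinib-everolimus combination) should be interrupted and the use of corticosteroids may be indicated until symptoms abate (resolved to CTCAE Grade 0-1". After a first event it allows, but does not require, restart at the doses used before. It says nothing about tolerability and does not mention Table 5. The Table 5 footnotes do not mention pneumonitis.

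**The concern.** Two current instructions cover the same event and direct opposite actions. A site that follows Table 5 literally keeps dosing a child whom Section 9.4.1.7 says to hold. That section itself describes pneumonitis as a recognised class effect of everolimus-type drugs, with some severe and, rarely, fatal cases. The synopsis carries Table 5 but not the pneumonitis rule, so someone working from the synopsis sees only the instruction to continue.

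There are two further consequences. For a first intolerable Grade 2 event, the text followed sets the lenvatinib dose from then on, because reductions are not normally reversed. In Phase 1, whether the drugs are held in Cycle 1 can affect whether the child counts as having a DLT. Two DLTs in a cohort of up to 6 mean the MTD has been exceeded, so one classification can matter.

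**Working it through.** The plan gives no figure to reproduce. The check sets the two texts side by side, using the starting level of 11 mg/m² lenvatinib and 3 mg/m² everolimus on which Table 5 is written.

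| Event | Table 5 | Section 9.4.1.7 | Can both be followed? |
|---|---|---|---|
| Grade 1 | Continue, no change | May continue, no adjustment | Yes, they agree |
| Grade 2, tolerable | Continue: 11 and 3 mg/m² daily | Hold both: 0 and 0 | **No** |
| Grade 2, intolerable, first event | Hold to Grade 0-1 or tolerable Grade 2; lenvatinib to 8 mg/m², everolimus unchanged | Hold to Grade 0-1; same doses permitted | Only by waiting for Grade 0-1 and not using the same-dose permission |
| Grade 2, intolerable, recurrent; or Grade 3 | Hold; reduce by occurrence | Hold to Grade 0-1; no restart dose given | Yes, by waiting for Grade 0-1 and taking the dose from Table 5 |
| Grade 4 | Discontinue | Discontinue | Yes, they agree |

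**Precedence.** Footnotes a to g of Table 5, the text above it and Section 9.4.1.7 contain no rule on which prevails. The SAP names pneumonitis only as an everolimus event of special interest (Section 5.6.2).

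**Dose after a first intolerable Grade 2 event.** Reduction under Table 5: 1 − 8/11 = 27.3%. If the 9.4.1.7 permission is used: 0%.

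**DLT status in Phase 1.** The inputs are a 28-day cycle, once-daily dosing, a DLT window of Cycle 1, and the non-hematological DLT list in the synopsis and Section 9.1. Planned dosage is taken as the 28 daily doses of Cycle 1. Two criteria depend on whether drug is held.

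- *Less than 75% of planned dosage.* 75% of 28 is 21 doses. Seven missed doses give 21/28 = 75.0%, which is not below the limit. Eight give 20/28 = 71.4%, which is. To lose 8 doses within Cycle 1 the hold must start by Day 28 − 8 + 1 = 21. Under Table 5 the same tolerable event gives 28/28.
- *Grade 2 toxicity lasting at least 7 days*, judged significant or intolerable enough to require interruption. This criterion has no dose-count threshold. An event held for 7 days can meet it while still at 75.0% of dosing. If Table 5 is followed and drug is continued, no interruption has been required.

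**The case against.** The strongest reply is that the drafting pattern shows the intent. Sections 9.4.1.2 to 9.4.1.17 are event-specific rules placed after Table 5. Where Table 5 should apply, many say so: PRES, diarrhea, hepatotoxicity, thromboembolic events and abdominal pain all send the reader back to it. Where the authors wanted something else, they wrote it: hypertension (9.4.1.3), arterial thromboembolism of any grade (9.4.1.11), gastrointestinal perforation of any grade (9.4.1.15) and QT prolongation (9.4.1.17). Section 9.4.1.7 is of the second kind, so a careful clinician would hold. This is the likely reading and it lowers the practical severity. It is not stated, however. The general sentence points to Table 5, and the synopsis and Section 9.1.4 add that a subject without intolerable toxicity can continue treatment.

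A second reply is that tolerability is a judgement. A physician could call Grade 2 pneumonitis intolerable, hold to Grade 0-1, reduce lenvatinib one level and so satisfy both texts. That route exists, but it uses Section 9.4.1.7 to settle a question that footnote c leaves to the subject and/or physician. It does not help once an event has been judged tolerable.

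Some stronger inferences are tempting and are not supported:

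- *The two texts conflict at every grade.* Grades 1 and 4 agree. The recovery thresholds are compatible, since waiting for Grade 0-1 meets both.
- *Eight missed doses is the DLT threshold.* That holds only for the 75% criterion. The Grade 2 criterion listed beside it can be met sooner.
- *A number of affected children follows from the 19% pneumonitis figure in 9.4.1.7.* That figure comes from the everolimus label. The documents give no rate for this pediatric regimen, no Grade 2 share and no tolerable share.

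**Conclusion.** The Table 5 row is wrong as written for treatment-related Grade 2 non-infectious pneumonitis judged tolerable. It continues full dosing where Section 9.4.1.7 holds both drugs, and no text says which governs. A smaller mismatch exists for a first intolerable Grade 2 event: 8 mg/m² lenvatinib directed, against 11 mg/m² permitted.

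Practical severity is modest, because sites will probably follow the specific section. It still merits correction, since the literal reading is the less safe one and is the only one in the synopsis. The DLT consequence is confined to Phase 1 Cycle 1. It operates through the two criteria above and remains a determination by the investigator and the medical monitor, in consultation with the PSC as needed. A reader might infer damage to the Phase 2 result, but the conflict does not alter the ORR definition, the two-stage boundaries, alpha or power. The figures rest on the 11 and 3 mg/m² starting level and uninterrupted once-daily dosing apart from the hold. No event rate or hold length is assumed.

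**What to change.** Add one footnote to both copies of Table 5 and a matching sentence in Section 9.4.1.7:

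*For non-infectious pneumonitis, Section 9.4.1.7 takes precedence over Table 5: interrupt both drugs for any Grade 2 event, regardless of tolerability, until Grade 0-1; the first restart may be at the same doses.*

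State alongside it that the other event-specific sections (for example 9.4.1.3, 9.4.1.11, 9.4.1.15 and 9.4.1.17) continue to apply as written. A sentence leaving Table 5 in force for all other events should be avoided, because it could undercut mandatory stops such as the one for arterial thromboembolism.

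Restart doses after recurrent Grade 2 or after Grade 3 should not simply be imported from Table 5. After a same-dose first restart it is unclear whether a recurrence counts as the first or second occurrence. The second-occurrence row gives 6 mg/m², which from 11 is a cut of 1 − 6/11 = 45.5%, or about 25% below the previous level, which is 0.75 × 11 = 8.25 mg/m². Footnote e would also resume everolimus unchanged after Grade 2, although 9.4.1.7 attributes pneumonitis to that drug's class. The sponsor should specify the occurrence count and which drug is reduced.

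The cost is one footnote and a short addition to 9.4.1.7 at the next amendment, with no extra data, visits or subjects.
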